Exploratory	To evaluate safety and tolerability of both: (a) Sunitinib and (b) Exercise testing	Eligibility rate, attrition rate, and adverse event rate (CTCAE v4.0) in each arm	See Section 11.5
Exploratory	To determine the dose intensity of sunitinib	Patient- reported drug diaries	See Section 11.5
Exploratory	To estimate early change in VO 2 peak at 4-5 weeks compared with baseline	Change in VO 2 peak from baseline to 4-5 weeks	See Section 11.5
Exploratory	To collect plasma angiome samples for analysis and correlation with primary and key secondary endpoints	Plasma angiome multiplex ELISA	See Section 11.5
Exploratory	To use real-time electronic monitoring to describe the following over the study period (subset of patients): 
 
(a) Changes in daily physical activity
 
(b) Changes in daily blood pressure
 
	
 
(a) Steps per day
 
(b) Daily blood pressure (mmHg) reading
 
	See Section 11.5

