## 9.1 Adverse Events (AEs)

An adverse event (AE) is any untoward medical occurrence in a subject receiving study drug and that does not necessarily have a causal relationship with this treatment. For this protocol, the definition of AE also includes worsening of any pre-existing medical condition. An AE can therefore be any unfavorable and unintended or worsening sign (including an abnormal laboratory finding), symptom, or disease temporally associated with the use of sunitinib, whether or not related to use of the sunitinib. Abnormal laboratory findings without clinical significance (based on the PI's judgment) should not be recorded as AEs. **Note:** Laboratory value changes that require therapy or adjustment in prior therapy are considered adverse events.

All non-serious adverse events will be collected from the time of first dose of study drug until the End of Treatment Visit. Serious adverse events that are related to study procedures are recorded from the time the informed consent form is signed until the End of Treatment Visit (or screen failure). These AEs must be recorded in the subject's medical record and adverse events case report form.

AEs will be assessed according to the Common Terminology Criteria for Adverse Events (CTCAE), version 4.0. If CTCAE grading does not exist for an AE, the severity of the AE will be graded as mild (1), moderate (2), severe (3), life-threatening (4), or fatal (5).

Attribution of AEs will be indicated as follows:

- Definite: The AE is clearly related to the study drug or exercise testing.
- Probably: The AE is likely related to the study drug or exercise testing.
- Possible: The AE may be related to the study drug or exercise testing.
- Unlikely: The AE is doubtfully related to the study drug or exercise testing.
- Unrelated: The AE is clearly NOT related to the study drug or exercise testing.

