### 9.1.1 AEs of Special Interest

“Fatigue” and “generalized muscle weakness” (regardless of site) are AEs of special interest. Care should be taken to appropriately identify, grade, and note the attribution of these AEs throughout the study. **Note:** There is no special reporting requirement for these AEs.

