### 9.1.2 Expected AEs with Exercise Testing (CPET)

Anticipated (expected) side-effects associated with a symptom-limited cardiopulmonary exercise test include:

- Fatigue
- Muscle soreness
- Joint pain
- Lower back pain
- Leg cramps

Unanticipated but possible side-effects that are rare, but serious include:

- Cardiovascular: angina, AV blocks, bradycardia, edema, hypotension, palpitations, rebound hypertension, shock, syncope
- Arrhythmias
- Myocardial ischemia
- Sudden cardiac death
- Cerebrovascular accident

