## 9.2 Serious Adverse Events (SAEs)

An AE is considered “serious” if in the opinion of the investigator it is one of the following outcomes:

- Fatal
- Life threatening
- Constitutes a congenital anomaly or birth defect
- A medically significant condition (defined as an event that compromises subject safety or may require medical or surgical intervention to prevent one of the three outcomes above).
- Requires inpatient hospitalization or prolongation of existing hospitalization
- Results in persistent or significant incapacity or substantial disruption to conduct normal life functions

SAE reporting criteria defined below

**A. Subset of SAEs Reportable for this Study.** Because the Pfizer Product used in this Study is a mature marketed product with a well-established safety profile, only SAEs that fit into any of the following categories need to be reported to Pfizer: (1) a death, regardless of whether it is considered related to treatment with the Pfizer Product, (2) a non-fatal SAE that occurs during the reporting period and that is assessed by the Principal Investigator as both related to treatment with the Pfizer Product and unexpected for that Product, (3) an SAE assessed by the Principal Investigator as related to the Pfizer Product that occurs after the SAE reporting period, or (4) an otherwise reportable event as described in paragraph B., below. An event should be considered "related" to the Pfizer Product if a relationship is at least a reasonable possibility, and "unexpectedness" should be based upon a single safety reference document identified by the Principal Investigator and documented in association with the study.

**B. Exposure During Pregnancy, Exposure During Lactation, Occupational Exposure, and Lack Of Effect.** Even though there may not be an associated SAE, exposure to the Pfizer Product during pregnancy, exposure to the Pfizer Product during lactation, and occupational exposure to the Pfizer Product are reportable, and lack of effect of the Pfizer Product may also be reportable.

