## 11.5 Secondary and Exploratory Objectives

For subjects with VO2 peak measures at week 4 or week 5, descriptive statistics including mean, standard deviation, minimum and maximum of VO2peak changes from baseline to week 4 and to week 5 will also be reported to assess early effects of each sunitinib schedule. Descriptive statistics for other secondary and exploratory endpoints will also be reported for each sunitinib schedule.

In addition, a random effects model will be used to assess the effect of different sunitinib schedules on the VO2 peak change. In the model repeated measurements of VO2 peak change at week 4, 5 and through week 12 from baseline are outcomes, schedule indicator (0 for schedule 4/2, 1 for schedule 2/1) is chosen as the main factor, baseline VO2 peak value and patient characteristics are other included covariates. Similarly, random effects models with other continuous repeated measures (i.e., resting and stress cardiac function and muscle strength) as dependent variables will also be used to analyze the schedule effects.

Sensitivity analyses will be performed for the primary endpoint and key secondary endpoint using Last Value Carried Forward (LOCF) methods. The intent of this sensitivity analysis is to assay the robustness of results observed in the modified ITT population.

Eligibility rate, acceptance rate and adverse event rate will be reported descriptively.

Eligibility rate is defined as the number of subjects eligible for the study divided by the number approached for the study (i.e., screen fail rate).

Acceptance rate is defined as the number of patients agreeing to participate divided by total number randomized.

Rates of adverse events, classified by CTCAE v4.0, will be displayed by body system and preferred term for each arm.

For analysis of the plasma angiome multiplex ELISA data, correlations among analytes will be evaluated by Spearman analysis. Analyte levels at baseline and changes on-treatment will be correlated with baseline VO2peak and changes in VO2peak, respectively.

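### For non-serious adverse events, a joint attribution to sunitinib or exercise testing means that the two parts of the exploratory safety objective cannot be reliably separated

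*Combined protocol and SAP*

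**What the plan says.** The exploratory objective in Section 4 reads "To evaluate safety and tolerability of both: (a) Sunitinib and (b) Exercise testing". Its endpoint is "Eligibility rate, attrition rate, and adverse event rate (CTCAE v4.0) in each arm".

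Section 9.1 defines five attribution levels. The top level is "Definite: The AE is clearly related to the study drug or exercise testing" and the bottom level is "Unrelated: The AE is clearly NOT related to the study drug or exercise testing". The three levels between them name the same two causes in the same joint form. Section 9.1.1 makes fatigue and generalized muscle weakness events of special interest and adds "Care should be taken to appropriately identify, grade, and note the attribution of these AEs throughout the study".

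For the analysis, Section 11.5 states: "Rates of adverse events, classified by CTCAE v4.0, will be displayed by body system and preferred term for each arm". It plans no display by attribution.

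Section 9.1 and footnote h of Table 3 start the collection of non-serious events at the first dose of sunitinib. SAEs related to study procedures are recorded from consent. For the baseline exercise visits, Section 8.2 lists SAEs only.

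**The concern.** The objective names two exposures, but the scale does not distinguish them. A grade of definite or possible says that one or the other caused the event, without saying which. If the scale is applied as written, the trial reports one pooled adverse event rate per arm. From that rate a reader can take neither a rate for exercise testing nor a clean rate for sunitinib.

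This matters for two reasons given in Section 3.3. Fatigue and muscular toxicity are central to the hypothesis, and later studies are to include exercise training, so the tolerability of maximal testing in these patients is useful output. Attribution is also a judgement made at the time of the event and is hard to reconstruct after database lock.

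**Working it through.** The plan gives no figure to reproduce here. The check compares the sections and then counts the tests affected.

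**Could anything else in the plan recover the cause of a non-serious event?**

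- *Randomization.* No. Under Section 5.1 both arms take sunitinib and every subject has the functional assessments at three time points. There is no group without testing and none without drug.
- *The event term.* Not for the terms that overlap. Section 9.1.2 introduces its list with "Anticipated (expected) side-effects associated with a symptom-limited cardiopulmonary exercise test include", and that list includes fatigue, joint pain and lower back pain. Section 3.2 lists fatigue, arthralgia and back pain among the common sunitinib reactions.
- *The analysis.* No. Section 11.5 stops at term and arm.
- *Onset relative to the test date.* Only in part. On schedule 4/2 without interruptions, the drug is taken on Days 1 to 28, so the Day 29 test falls on the first day off. On schedule 2/1 it is taken on Days 1 to 14 and 22 to 35, so the Day 36 test also falls on the first day off. Drug effects are plausible at both. Day 85 is clearer: 84 = 2 × 42 = 4 × 21, so that test follows a scheduled break of 14 days (4/2) or 7 days (2/1). However, non-serious collection ends at the End of Treatment Visit, nominally due by Day 85. Delayed effects of the last test may therefore be missed, depending on how the visits are scheduled.

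**Are serious events in the same position?** Largely not. Section 9.2 has SAEs "assessed by the Principal Investigator as both related to treatment with the Pfizer Product and unexpected for that Product", a judgement about the drug alone. Section 9.2.1 requires the causal relationship to the drug in the SAE documentation. Section 9.1 identifies SAEs related to study procedures separately.

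**How many tests are affected?** Inputs: 30 evaluable patients (Section 11.6), CPET at baseline, Day 29 or 36, and Day 85 (Table 3), and non-serious collection from first dose (Section 9.1).

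- CPETs after first dose: 2 × 30 = 60.
- Baseline CPETs, all before sunitinib: 1 × 30 = 30. Their non-serious events cannot be confused with drug effects, but they are not collected either.
- Strength sessions after first dose: Table 3 marks two (Day 29 or 36, and Day 85), while the Section 8.5 list omits strength testing at Day 29 or 36. The count is therefore 1 × 30 = 30 to 2 × 30 = 60.

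**What would a rate per test look like?** If all 90 CPETs formed the denominator while non-serious events came only from the 60 after first dose, the rate would be 60/90, about two thirds, of the rate in the tests actually observed.

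**The case against.** The strongest reply is that Section 9.1 defines levels and does not say that each event gets a single entry. The adverse event CRF is not in the documents, and a site could apply the scale once per cause. This stands as far as it goes: a reader might infer that every event carries exactly one attribution, and the text does not establish that. But no section asks for two entries, and two sites could both follow the text and record different things.

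A reader might also infer that the objective cannot be answered at all, or that exercise testing gets no numerator. Neither is supported. The endpoint is an event rate per arm, which Section 11.5 delivers without attribution. SAEs are separable by cause, and these include the grave exercise risks in Section 9.1.2 where they meet the SAE definition. What remains is that a pooled rate of non-serious events does not evaluate the two parts individually.

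Nor do the documents support reading all 90 scheduled CPETs as having mixed attribution, since 30 of them precede the drug.

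Three further limits are fair. Section 5.1.1 leaves dose decisions for toxicities unrelated to sunitinib to the investigator, and nothing ties those decisions to the recorded code. Fatigue is also measured by FACIT-F, which uses no attribution, and both arms have the same number of scheduled CPETs, so no bias in the fatigue comparison between schedules follows from this point. Finally, an investigator with two fields would still sometimes be unsure about fatigue. The fields record that judgement; they do not remove the doubt.

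**Conclusion.** The point holds for non-serious events. As written, the plan specifies neither a cause-specific attribution nor an analysis by cause, so the sunitinib and exercise-testing parts of the objective cannot be reliably separated. Fatigue, joint pain and back pain are the terms most exposed.

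The reach is about 60 on-treatment CPETs and 30 to 60 on-treatment strength sessions. In addition, non-serious events go unrecorded at the 30 baseline CPETs, where the drug could be excluded as a cause. These counts assume 30 completers who attend every scheduled test; patients who drop out would add some. The conclusion also assumes that the CRF follows the scale in Section 9.1. If the CRF already holds separate fields, the remaining gaps are the protocol wording, the missing table and the baseline window.

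The objective is exploratory and the primary and key secondary analyses are unaffected. The change is worth making before data collection but is not critical to the trial.

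**What to change.** - In Section 9.1 and on the adverse event CRF, record two attributions per event on the existing five-level scale: one to sunitinib and one to exercise testing. State that exercise testing covers the CPET with its stress echocardiogram and the strength and endurance tests.
- In Section 11.5, tabulate adverse events by arm for each attribution.
- For an exercise-testing rate per test, choose one of two consistent options. Either collect non-serious exercise-related events from the first baseline exercise test, amending Sections 8.2 and 9.1 and footnote h of Table 3, or restrict the denominator to tests done after first dose. The first option also uses the drug-free tests.

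The cost is one extra CRF field per event, a short protocol edit and one extra table. Extending the window adds a little event recording at baseline. No visit, test or clinical rule changes.

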### 9.1.1 AEs of Special Interest

“Fatigue” and “generalized muscle weakness” (regardless of site) are AEs of special interest. Care should be taken to appropriately identify, grade, and note the attribution of these AEs throughout the study. **Note:** There is no special reporting requirement for these AEs.

### 9.1.2 Expected AEs with Exercise Testing (CPET)

Anticipated (expected) side-effects associated with a symptom-limited cardiopulmonary exercise test include:

- Fatigue
- Muscle soreness
- Joint pain
- Lower back pain
- Leg cramps

Unanticipated but possible side-effects that are rare, but serious include:

- Cardiovascular: angina, AV blocks, bradycardia, edema, hypotension, palpitations, rebound hypertension, shock, syncope
- Arrhythmias
- Myocardial ischemia
- Sudden cardiac death
- Cerebrovascular accident

## 9.2 Serious Adverse Events (SAEs)

An AE is considered “serious” if in the opinion of the investigator it is one of the following outcomes:

- Fatal
- Life threatening
- Constitutes a congenital anomaly or birth defect
- A medically significant condition (defined as an event that compromises subject safety or may require medical or surgical intervention to prevent one of the three outcomes above).
- Requires inpatient hospitalization or prolongation of existing hospitalization
- Results in persistent or significant incapacity or substantial disruption to conduct normal life functions

SAE reporting criteria defined below

**A. Subset of SAEs Reportable for this Study.** Because the Pfizer Product used in this Study is a mature marketed product with a well-established safety profile, only SAEs that fit into any of the following categories need to be reported to Pfizer: (1) a death, regardless of whether it is considered related to treatment with the Pfizer Product, (2) a non-fatal SAE that occurs during the reporting period and that is assessed by the Principal Investigator as both related to treatment with the Pfizer Product and unexpected for that Product, (3) an SAE assessed by the Principal Investigator as related to the Pfizer Product that occurs after the SAE reporting period, or (4) an otherwise reportable event as described in paragraph B., below. An event should be considered "related" to the Pfizer Product if a relationship is at least a reasonable possibility, and "unexpectedness" should be based upon a single safety reference document identified by the Principal Investigator and documented in association with the study.

**B. Exposure During Pregnancy, Exposure During Lactation, Occupational Exposure, and Lack Of Effect.** Even though there may not be an associated SAE, exposure to the Pfizer Product during pregnancy, exposure to the Pfizer Product during lactation, and occupational exposure to the Pfizer Product are reportable, and lack of effect of the Pfizer Product may also be reportable.

### 9.2.1 Reporting of SAEs

Serious adverse events, whether or not considered drug related, should be reported within 24 hours of becoming aware of the event, using the provided DCI SAE Report Form and the SAE Report Review Form (Site Assessment). These documents should be sent to:

- The DCI Safety Desk – [contact]; [contact]; email: [[contact]](mailto:[contact])

**Note:** If the DCI Safety Desk cannot be reached within 24 hours, the Principal Investigator should be contacted:

- [name], [contact]; [contact]; email: [[contact]](mailto:[contact])

The initial report for each SAE or death should include at minimum the following information:

- Protocol # and title
- Patient initials, study identification number, sex, age
- Date the event occurred
- Description of the SAE
- Dose level and cycle number at the time the SAE occurred
- Description of the patient's condition
- Indication whether the patient remains on study

- Causality

Follow-up information including severity, action taken, concomitant medications, and outcome should be communicated to Duke as soon as possible.

Upon receipt of the DCI SAE Report form by the DCI Safety Desk, the PI will be notified and be required to complete the PI assessment of the DCI SAE Report Review Form. The DCI Safety Desk will, in turn, report the event to Pfizer if the SAE is felt to be at least possibly related to sunitinib using the DCI SAE Report Form. The *Reportable Event Fax Cover Sheet* provided by Pfizer must also be included with each SAE submitted.

The SAE documentation, including the DCI SAE Report Form and available source records, should be faxed to Pfizer per the instructions on the SAE cover sheet.

The following minimum information is required for this documentation and report:

- Study number/IIT regulatory identifier
- Subject number, sex, and age
- Report date
- SAE description (event, seriousness of the event)
- Causal relationship to the study drug

Follow-up information for the event should be sent promptly (within 7 days) as necessary.

### **9.3 Procedure in Case of Pregnancy**

Sunitinib is Pregnancy Category D.

Sunitinib can cause fetal harm when administered to a pregnant woman. As angiogenesis is a critical component of embryonic and fetal development, inhibition of angiogenesis following administration of sunitinib should be expected to result in adverse effects on pregnancy. In animal reproductive studies in rats and rabbits, sunitinib was teratogenic, embryotoxic, and fetotoxic.

Subjects receiving sunitinib are advised to use 2 acceptable methods of birth control (one of which must include a condom as a barrier method of contraception) starting at the time of screening and continuing throughout the course of treatment and for at least three months after sunitinib is discontinued.

If, during the conduct of the clinical trial, a male subject impregnates his partner, OR a female subject becomes pregnant, the subject should report the pregnancy to the Investigator. With the permission of the pregnant partner, the Investigator should report the pregnancy to Pfizer as an SAE within 24 hours of awareness of the event. The expected date of delivery or expected date of the end of the pregnancy, last menstruation, estimated fertility date, pregnancy result, and neonatal data, etc., should be included in this information.

With the permission of the pregnant partner, the Investigator should report the outcome of the pregnancy (independent of outcome, e.g., full-term delivery, pre-term delivery, spontaneous abortion, induced abortion, stillbirth, death of newborn, congenital anomaly [including anomaly in a miscarried fetus, etc.]) in accordance with the same reporting procedure as for SAEs (see **Section 9.2.1**). The date of outcome of the pregnancy,

gestational age, date of birth, and neonatal data, etc., should be included in this information. Informed consent will need to be obtained from the pregnant partner to document her permission to disclose this information to Pfizer.

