11. For women of childbearing potential (WOCBP) must have a negative serum pregnancy test prior to the start of the study. Women of childbearing potential (WOCBP) must agree to follow instructions for method(s) of contraception for the duration of the study. Medically acceptable contraceptives include: (1) surgical sterilization (such as a tubal ligation or hysterectomy), (2) approved hormonal contraceptives (such as birth control pills, patches, implants or injections), (3) barrier methods (such as a condom or diaphragm) used with a spermicide, or (4) an intrauterine device (IUD). Contraceptive measures such as Plan B (TM), sold for emergency use after unprotected sex, are not acceptable methods for routine use. If you do become pregnant during this study or if you have unprotected sex, you must inform your study physician immediately.

12. For men who are sexually active, must agree to use a two medically acceptable forms of birth control (one of which must include a condom as a barrier method of contraception) in order to be in this study. Medically acceptable contraceptives include: (1) surgical sterilization (such as a vasectomy), or (2) a condom used with a spermicide. Contraceptive measures such as Plan B (TM), sold for emergency use after unprotected sex, are not acceptable methods for routine use. Men must also agree to inform their partner of the potential for harm to an unborn child. She should know that if pregnancy occurs, the subject will need to report it to the study doctor, and she should promptly notify her doctor. The study doctor will ask if the subject's partner is willing to provide updates on the progress of the pregnancy and its outcome. If the subject's partner agrees, this information will be provided to Pfizer, Inc. for safety monitoring follow-up.

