## 8 SCREENING, REGISTRATION, AND ON-STUDY TESTS AND PROCEDURES

In addition to assessment for the **primary** endpoint ( $VO_2$ peak) by cardiopulmonary exercise testing (CPET), **secondary** and **exploratory** assessments for functional capacity, quantitative skeletal muscle function, patient-reported outcomes, and other endpoints will occur throughout the study as specified in Table 3, Schedule of Events.

The important time periods [and windows] during the study include:

- **Screening** on Day -84 to -1
- **Exercise Testing A [Day -28 to -1]**
- **Exercise Testing B [Day -28 to -1, at least 24 hours before or after the CPET as part of Exercise Testing A]**
- **Randomization on Day -1 [Day -28 to -1], may occur on the same day as Exercise Testing B but after Inclusion/Exclusion criteria have been completed**
- **Treatment Period:** Sunitinib from Day 1 to 85
- **End of Treatment Visit** either 30 days after the last dose of sunitinib or on Day 85, whichever occurs first. (There is no Safety Follow Up Visit in this study because the vast majority of patients are expected to continue sunitinib beyond Day 85 per standard of care.)

All subjects will receive treatment with sunitinib according to the schedule to which they are randomized.

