## 8.7 Off Study and End of Study

The End of Treatment Visit will occur approximately 30 days after the last dose of sunitinib or on Day 85, whichever occurs first. **Note:** There is no Safety Follow Up Visit in this study because the vast majority of patients are expected to continue sunitinib beyond Day 85 per standard of care (see **Table 3. Schedule of Events**).

A subject is considered off study when he/she has completed the End of Treatment Visit. All subjects discontinuing study drug for any reason will have an End Of Treatment Visit approximately 30 days after their last dose of study drug or prior to initiation of cytotoxic or investigational therapy, whichever occurs first.

Reasonable effort should be made to contact any subject lost to follow-up during the course of the study in order to complete study-related assessments and retrieve any outstanding data and study drug. Following unsuccessful telephone contact, an effort to contact the subject by mail using a method that provides proof of receipt should be attempted. Such efforts should be documented in the source documents.

The end of the study will occur when the last enrolled subject has completed his/her End of Treatment Visit. A database lock will occur when the data has been cleaned to the specifications in the data quality plan. The database will then be frozen, and no further changes will be permitted.

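### For women of childbearing potential, inclusion criterion 11 and Section 9.3 differ on how long contraception lasts, how many methods are meant, and whether it is required or advised

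*Combined protocol and SAP*

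**What the plan says.** Three places in the protocol set contraception rules.

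- **Section 7.1, criterion 11 (women).** "Women of childbearing potential (WOCBP) must agree to follow instructions for method(s) of contraception for the duration of the study". It then lists what counts as medically acceptable: surgical sterilization, hormonal contraceptives, a barrier with spermicide, or an IUD. The four options are joined by a single 'or'. No minimum number is given and a condom is not required.
- **Section 7.1, criterion 12 (sexually active men).** They "must agree to use a two medically acceptable forms of birth control", one of which has to be a condom. No end point is given.
- **Section 9.3 (all subjects).** "Subjects receiving sunitinib are advised to use 2 acceptable methods of birth control", one of them a condom, starting at screening and "continuing throughout the course of treatment and for at least three months after sunitinib is discontinued". The same section says that sunitinib can cause fetal harm and was teratogenic in rats and rabbits.

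Two further statements fix the time frame. Section 8.7 says: "A subject is considered off study when he/she has completed the End of Treatment Visit". That visit falls about 30 days after the last dose or on Day 85, whichever comes first. Section 8 gives as the reason for having no safety follow-up visit that "the vast majority of patients are expected to continue sunitinib beyond Day 85 per standard of care".

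**The concern.** Criterion 11 is the rule that staff verify before enrolment (Sections 8.1.1.1 and 8.1.1.2). Section 9.3 sits under a heading about what to do when a pregnancy occurs, which a site is likely to open only after the event. The rule checked at entry is therefore the shorter and looser one, and the longer and fuller one is phrased as advice in a less visible place.

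At stake is fetal exposure to a drug that the protocol itself describes as teratogenic. A woman can meet the eligibility criterion in full and still fall outside what Section 9.3 describes, both during the study and after it. A site has no text telling it which level it must hold her to. No analysis, sample size or endpoint is affected.

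**Working it through.** The plan gives no figure to reproduce. The check compares the texts and counts days.

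**Inputs**

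- *d*: study day of the last sunitinib dose.
- End of the criterion 11 period, taken as the subject's own time on study (Section 8.7): min(*d* + 30, 85).
- Earliest end of the Section 9.3 period: *d* + 90, with three months taken as about 90 days (assumption; the range is 90 to 92).
- Planned dosing days (Section 5.1). On 4/2, the second four-week course runs from Day 43 to Day 70. On 2/1, the fourth two-week course runs from Day 64 to Day 77.

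**Duration**

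Gap = (*d* + 90) − min(*d* + 30, 85).

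| Last dose | Criterion 11 ends | Section 9.3 ends, earliest | Gap |
|---|---|---|---|
| By Day 55 | *d* + 30 | *d* + 90 | about 60 days |
| Day 70 (end of second 4/2 course) | Day 85 | 70 + 90 = Day 160 | about 75 days |
| Day 77 (end of fourth 2/1 course) | Day 85 | 77 + 90 = Day 167 | about 82 days |
| After Day 85 | Day 85 | later than 85 + 90 = Day 175 | more than 90 days, no upper limit |

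Using 92 days adds 2 days to each gap. The visit windows (±3 days for Day 85, ±7 days for the End of Treatment Visit) move a gap by at most 7 days. The smallest would then be 60 − 7 = 53 days, so none closes. In the last row, which the protocol expects for most patients, the criterion 11 period ends while the woman is still taking sunitinib.

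**Number of methods**

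- Women: criterion 11 states no number, and its list can be read as satisfied by one option, for example an IUD alone. Section 9.3 refers to two methods, one a condom. On that reading the two differ.
- Men: criterion 12 and Section 9.3 both give two methods including a condom. They agree.

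**Binding force**

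Criterion 11 is a condition of entry. Section 9.3 is worded as advice, although its parenthesis about the condom is phrased as a requirement.

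**Can both be followed?**

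Yes. A woman who uses two acceptable methods including a condom, from screening to at least three months after sunitinib, has also used acceptable contraception throughout the study. The reverse does not follow: criterion 11 can be met with one method that stops at the End of Treatment Visit.

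**The case against.** The strongest reply is that the rules are nested: criterion 11 is a minimum for entry and Section 9.3 is the fuller instruction. This is correct as far as it goes. A reader might infer that sites cannot follow both texts, but the documents do not support that, because following Section 9.3 satisfies both. What remains is that the entry criterion does not secure the fuller instruction and does not point to it.

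Second, Section 9.3 only advises, so a woman who falls short of it breaches no criterion. That is true, and it is part of the inconsistency: the shorter rule binds and the longer one does not.

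Third, criterion 11 asks women to follow instructions on method or methods, which leaves room for Section 9.3 to supply the number. This is a fair reading. The difference in number is inferred from the list of alternatives, not stated, and it is weaker than the difference in duration.

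Fourth, treatment after Day 85 is standard of care with commercial drug (Section 6.3), so a criterion limited to the study is unsurprising, and Section 9.3 already covers the later period. Patients are therefore not left without any protocol guidance after Day 85. But the first three rows of the table involve only sunitinib taken on study, and the gap is still about 60 to 82 days.

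Fifth, the consent form may state the Section 9.3 period. It was not available for this review, so nothing is alleged about what patients are told.

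A reader might also infer a conflict for men. There is none on number of methods. Criterion 12 is silent on duration, and Section 9.3 supplies one for all subjects receiving the drug.

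**Conclusion.** The concern holds for women of childbearing potential as an inconsistency between criterion 11 and Section 9.3 in duration, number of methods and binding force. Duration is the firmest part. The criterion 11 period ends about 60 to 82 days before the Section 9.3 period at the on-study last-dose days examined, and more than 90 days before it when sunitinib continues past Day 85. For men the only defect is a missing duration in criterion 12.

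The figures rest on two assumptions. Three months is taken as about 90 days. The duration of the study is taken as the subject's own participation; Section 8.7 also defines an end of the whole study, at the last subject's End of Treatment Visit. If criterion 11 meant that date, the gap would vary with enrolment date and could not be stated in advance.

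The number of women affected is unknown. Planned accrual is 36 (Section 11.6), and the documents give no count of women of childbearing potential. The point should be corrected because it bears on patient safety, but it does not touch the statistical analysis.

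**What to change.** Reconcile criterion 11 with Section 9.3 on three items: how long contraception continues, how many methods are meant and whether a condom is among them, and whether the rule is required or advised. State the end point in terms that cannot be read two ways. Give criterion 12 a duration consistent with the reconciled Section 9.3, for example by cross-reference; its number of methods already matches the current text. Then check that the consent form says the same. Which version applies is for the sponsor to decide; this review takes no view.

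The cost is an amendment to wording in up to three places, plus the consent form if it does not match. Sample size, data collection and analysis are unchanged.
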